# 10.3.1 Primary Efficacy Endpoint

The primary efficacy endpoint is the change in 6MWD measured at peak exposure (defined as 10 to 60 minutes after dosing) after 12 weeks of study drug treatment. The primary endpoint analysis will evaluate the difference in baseline-corrected 6MWDs between active and placebo conditions. The primary endpoint analysis will test the hypothesis of an improvement in baseline-corrected 6MWDs for active compared to placebo conditions as administered to subjects with PH-COPD. The primary null hypothesis to be tested is that there are no differences in the baseline-corrected 6MWDs between active and placebo conditions.

A mixed-effect model repeated measure will be used to estimate the treatment effect. The magnitude of treatment effect will be estimated across the 12-week conditions between 2 treatment groups and the test of the Week 12 treatment effect will be produced using contrasts.

Sensitivity analyses to support the primary endpoint analysis will be conducted to examine robustness of results under various assumptions underlying the analysis (eg, normality, effects of dropout).

# 10.3.2 Alternate Primary Efficacy Endpoint

The analysis strategy will be specified a priori with details fully documented in the SAP prior to the unblinding of the study.

#### 10.3.3 Secondary Efficacy Endpoint(s)

The effect of inhaled treprostinil after 12 weeks of treatment will be formally tested on the following secondary efficacy endpoints:

- 1. Change in MVPA as measured by actigraphy
- 2. Change in overall activity as measured by actigraphy
- 3. Change in Borg dyspnea score from baseline
- 4. Change in 6MWD/Borg dyspnea composite score from baseline
- 5. Change in QOL from baseline as measured by SGRQ and UCSD SOBQ

- 6. Change in plasma concentration of NT-proBNP from baseline
- 7. Change in PGA

Hypothesis testing of secondary efficacy endpoints will be conducted using a gatekeeper strategy, such that any secondary endpoints will be considered for statistical significance only if the primary endpoint is statistically significant. Under closed testing procedures, the Type I family-wise error rate will be controlled at the 0.05 level of significance. The SAP will detail the specific analyses and methods for testing of secondary efficacy endpoints.

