7 GENERAL CONSIDERATIONS FOR DATA ANALYSES

Given the crossover design utilized for this study, efficacy and safety summary tables will follow the general format that baseline and post-baseline data will be presented by the assigned treatment condition when those data are observed during the treatment period. Treatments will be labeled as “Treprostinil” and “Placebo” to correspond with the assigned treatment condition.

Any efficacy and safety data that are collected during the washout period between Periods 1 and 2 will be presented for the assigned treatment condition from Period 1. Any follow-up data collected after Period 2, while on this study, will be assigned to Period 2. Subjects who are not retained will not be replaced during the study.

For continuous variables, the summary statistics will include the mean, standard deviation, median, lower quartile, upper quartile, minimum, and maximum. Statistics will be expressed using the level of precision in which the variable was collected. For discrete variables, summaries will include the frequency and percent in each category. Whenever practical, categories of discrete variables will be ordered and labeled as they appear in the case report form (CRF), and all categories represented on the CRF will be included in summaries, even when they do not apply to any patients in the study.

For data collected on a fixed schedule, the nominal time point will be used for summarization. Evaluations from Unscheduled Visits are to be mapped to Scheduled Visits to the extent possible per the protocol-specified windows. Repeat or redundant observations within an assessment window and observations that do not fall within any predefined assessment window will be excluded from summaries. If an evaluation is repeated, such as to confirm an observed aberrant laboratory value, the analyses will use the later value if within the protocol-specified window.

Unless otherwise specified, all final statistical tests will be 2-sided at alpha level 0.05 if the interim analysis is not conducted, and 0.022, if conducted. All tables will be presented in landscape format. For practical reasons, the point size may be reduced to (but not less than) 7 point for tables that contain too much information to fit into a single page. SAS[®] version 9.4 or higher will be used. The Sponsor's Biostatistics Department will analyze the efficacy and safety data.

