7.7 MULTIPLE COMPARISONS AND MULTIPLICITY

A gatekeeper strategy will be employed to address multiple comparisons. Secondary endpoints will be formally tested only if the primary endpoint is statistically significant. If the primary analysis of treprostinil vs placebo change from Baseline to Week 12 is statistically significant at a 2-sided alpha level of 0.05, showing superiority of treprostinil over placebo, then the secondary endpoints will be formally tested.

[REDACTED]

- [REDACTED]
- [REDACTED]
- [REDACTED]
- [REDACTED]
- [REDACTED]

[REDACTED]

Other secondary endpoints, including change in QOL, based on the SGRQ and UCSD SOBQ, and PGA will not have formal statistical testing.

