9.3 KEY SECONDARY EFFICACY MEASURES

The following secondary endpoints will be formally tested (in order) if the primary endpoint analysis is statistically significant. Each will assess if inhaled treprostinil improves the endpoint at Week 12 over placebo in subjects with PH-COPD. Improvement is defined as a decrease in the NT-proBNP plasma concentration, an increase in MVPA, an increase in overall activity, decrease in Borg dyspnea score, and an increase in the rank for the 6MWD and Borg dyspnea composite score. The null and alternative hypotheses are:

$$H_0: \mu_1 = \mu_2$$

$$H_a: \mu_1 < \mu_2 \text{ or } \mu_1 > \mu_2, \text{ dependent on the stated direction above,}$$

where μ_1 and μ_2 are inhaled treprostinil and placebo treatments, respectively.

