9.4 OTHER SECONDARY EFFICACY MEASURES

9.4.1 St. George's Respiratory Questionnaire

The SGRQ is a 50-item questionnaire designed to measure impact on overall health, daily life, and perceived wellbeing in patients with obstructive airways disease (Jones 1992). Scores for the SGRQ are totaled into 3 components (symptoms, activities, impacts) as well as a total score. Scores weighted and expressed as a range from 0 to 100, with higher scores indicating more limitations. The current established minimal important difference for SGRQ scores in an average COPD population is -4 units (Jorrit 2015). Calculation of component and total scores are described in the manual (Jones 2009).

Descriptive statistics for the raw and change from baseline to Week 12 values for the SGRQ the components and the total score will be presented for each scheduled visit by treatment.

Additionally, boxplots presenting the raw values and changes from baseline for each visit will be presented. The SGRQ scores will be treated as a continuous variable.

A longitudinal mixed model will be used to describe the change from baseline for the each of the scores over time. All subjects, including those who did not complete both treatment sequences, will be included in the model. A contrast will be calculated for Week 12 to compare the treatment groups with respect to change. The outcome variable will be change from baseline. Independent variables will be treatment, the subject's baseline average SGRQ score, treatment sequence, visit number, and the interaction of visit and treatment.

Observed values for the FAS and PPROT will be used with no imputation for missing values.

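### SAP 7.7 drops SGRQ, UCSD SOBQ and PGA from the formal testing that Protocol 10.3.3 commits to, without flagging the change; the two questionnaires can be restored at the end of the sequence at no alpha cost

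*Protocol*

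**What the plan says.** Protocol 10.3.3 opens its list of seven secondary endpoints with "The effect of inhaled treprostinil after 12 weeks of treatment will be formally tested on the following secondary efficacy endpoints". Item 5 is "Change in QOL from baseline as measured by SGRQ and UCSD SOBQ" and item 7 is PGA. The same section adds: "Under closed testing procedures, the Type I family-wise error rate will be controlled at the 0.05 level of significance". It leaves the detailed analyses and testing methods to the SAP.

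SAP 2.4 still lists all seven. SAP 7.7 then says: "Other secondary endpoints, including change in QOL, based on the SGRQ and UCSD SOBQ, and PGA will not have formal statistical testing". SAP 9.3 covers five endpoints (MVPA, overall activity, Borg, the 6MWD/Borg composite, NT-proBNP): "The following secondary endpoints will be formally tested (in order) if the primary endpoint analysis is statistically significant". The three excluded instruments appear in SAP 9.4 as other secondary measures.

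SAP 9.4.1 and 9.4.2 nonetheless fit longitudinal mixed models for SGRQ and UCSD SOBQ; for SGRQ, "A contrast will be calculated for Week 12 to compare the treatment groups with respect to change", and 9.4.2 plans the same for UCSD SOBQ. SAP 9.4.4 gives PGA descriptive statistics only.

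Appendix 12.4 does not modify 7.7, so the exclusion also applies under the Contingent Parallel Design. Protocol section 10 allows statistical methods to be changed before database lock without an amendment, and says that such changes will be documented in the SAP.

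**The concern.** The two documents give opposite answers on whether three instruments are formally tested. The readable SAP text does not identify 7.7 as a departure from Protocol 10.3.3 and gives no reason for it.

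Two of the protocol's seven secondary items (5 and 7) lose formal status. The item that matters most is quality of life. Even if the primary and all five key secondaries succeed, the trial cannot make a multiplicity-controlled statement on SGRQ or UCSD SOBQ, although models and Week 12 contrasts are planned for both and the SAP quotes minimal important differences for them (4 and 5 units). Protocol 10.3 ties experiment-wise error control to labeling, so formal status has consequences. On the readable text the exclusion protects nothing, because endpoints tested last take no alpha from those ahead of them.

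**Working it through.** **1. The plan's error rate.** Protocol 10.3.3 sets family-wise error at 0.05, and SAP 9.3 tests five endpoints in order after the primary. If each step is a two-sided test at 0.05 and testing stops at the first failure, a false rejection requires rejecting the first true null in the order, so the error is at most 0.05. In a simulation (400,000 runs per scenario; common correlation 0, 0.5 or 0.9; first true null at each of positions one to six), the error was 0.0494 to 0.0507. The Monte Carlo standard error is √(0.05 × 0.95 / 400,000) ≈ 0.0003. The plan's figure reproduces.

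**2. Adding two endpoints strictly last.** Let H1 to H6 be the primary and five key secondaries, H7 SGRQ total and H8 UCSD SOBQ total. H7 is tested only if H1 to H6 are all rejected, and H8 only if H7 is rejected too.

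- If any of H1 to H6 is true, rejecting H7 or H8 requires that true null to have been rejected already. The probability of at least one false rejection does not change.
- If H1 to H6 are all false, the first true null among H7 and H8 is tested once, at level α. The error is at most α.

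The argument does not use the method applied to H1 to H6; it needs only that this method holds its own error at α. It therefore survives the redaction in SAP 7.7, provided the additions come strictly last. In simulation with three steps added (SGRQ, UCSD SOBQ and PGA, one more than proposed), the error was 0.0492 to 0.0508. Decisions on the first six hypotheses were identical in all 200,000 runs compared. By contrast, two independent tests at 0.05 outside any sequence would give 1 − 0.95² = 0.0975.

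**3. The chance of a formal conclusion.** As written it is zero. The documents give no power for the secondary endpoints, so the following is an assumed range: primary power 90% (the design figure in both sample-size statements), the same power p at every later step, and every test at 0.05. For independent endpoints:

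- SGRQ (step 7): 0.9 × p⁶
- UCSD SOBQ (step 8): 0.9 × p⁷

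The values at correlation 0.5 come from simulation.

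| p per step | SGRQ, independent | UCSD SOBQ, independent | SGRQ, corr. 0.5 | UCSD SOBQ, corr. 0.5 |
|---|---|---|---|---|
| 0.5 | 0.014 | 0.007 | 0.142 | 0.124 |
| 0.7 | 0.106 | 0.074 | 0.328 | 0.301 |
| 0.8 | 0.236 | 0.189 | 0.469 | 0.442 |
| 0.9 | 0.478 | 0.430 | 0.656 | 0.634 |

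**4. Readiness of each instrument.**

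- SGRQ: SAP 9.4.1 models three components and the total, so one score must be named.
- UCSD SOBQ: SAP 9.4.2 already uses a single total score.
- PGA: no model, two items, and a scale that differs between documents (5 points in SAP 9.4.4, seven response options in Protocol 15.5). It is not ready for a formal test.
- Parallel design: Appendix 12.4.6 keeps treatment sequence in the SGRQ and UCSD SOBQ models, whereas 12.4.4 removes it from efficacy analyses.

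**5. The level passed down.** SAP 7.7 opens the secondary tests when the primary is "statistically significant at a 2-sided alpha level of 0.05, showing superiority of treprostinil over placebo, then the secondary endpoints will be formally tested". SAP 7 says that "all final statistical tests will be 2-sided at alpha level 0.05 if the interim analysis is not conducted, and 0.022, if conducted". If the interim is run, these disagree.

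**The case against.** The documents settle which text governs. Protocol section 10 allows the change, Protocol 10.3.3 delegates testing details to the SAP, and the SAP is consistent within itself: 7.7, 9.3 and 9.4 draw the same line between key and other secondaries. Estimating a contrast outside the confirmatory family is ordinary practice, and restricting that family to five endpoints is not a statistical error. The body of 7.7 and much of the preface are redacted, so a rationale may exist there. The benefit depends on six prior successes. Promotion also needs tidying, and SGRQ and UCSD SOBQ use observed values only, whereas 6MWD and Borg take worst scores for death or being too ill to walk.

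Most of this stands, and it rules out some stronger readings that a reader might infer:

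- That the SAP breaches the protocol: section 10 permits the change.
- That the status of these p-values is open to choice after unblinding: 7.7 is explicit and governs, so that risk is small.
- That the trial could say nothing about dyspnea: Borg and the composite remain formally tested, and SGRQ and UCSD SOBQ estimates are still reported.
- That the sponsor had no reason: redacted text cannot be read that way.

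The objection does not remove the visible mismatch, which the readable SAP leaves unrecorded although Protocol section 10 says that changes will be documented there. Nor does it identify anything gained by leaving the two questionnaires out of the end of the sequence.

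**Conclusion.** The point holds as an undocumented narrowing, on the readable text, of the protocol's testing plan. Three instruments, covering two of seven secondary items, lose formal testing. The recoverable loss is one item: a multiplicity-controlled conclusion on SGRQ and UCSD SOBQ. Restoring it costs the earlier endpoints no alpha and no power, on the single condition that the additions are tested only after the primary and all five key secondaries are rejected. That no alpha is lost does not mean the chance of success is high: the 1% to 66% range for SGRQ rests wholly on assumed powers and correlations. The change is worth making, but the primary analysis does not depend on it.

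**What to change.** Before database lock:

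- In SAP 7.7 and 9.3, add SGRQ total score and then UCSD SOBQ total score as the last two steps, using the Week 12 contrasts in 9.4.1 and 9.4.2. Keep the SGRQ components descriptive.
- Narrow the exclusion sentence in SAP 7.7 to PGA. Change Protocol 10.3.3 to say that PGA is summarised descriptively, and reconcile the PGA scale between SAP 9.4.4 and Protocol 15.5.
- State the alpha passed down the sequence if the interim is run, resolving 0.05 in SAP 7.7 against 0.022 in SAP 7, and say how secondaries are tested if the trial stops early. Appendix 12.4.2 gives 0.044 for the parallel design's final analysis at exactly 75% information, so cover both designs.
- Remove treatment sequence from the SGRQ and UCSD SOBQ models in Appendix 12.4.6, to agree with 12.4.4.

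If the sponsor prefers five formally tested endpoints, the minimum is a sentence in the SAP recording and justifying the departure from Protocol 10.3.3.

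The cost is a few lines of text, with no new data or models and no effect on the first six tests. The downside is that a non-significant SGRQ or UCSD SOBQ result, once reached, is a formal negative.

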# 10.3.4 Safety Analyses

The safety of inhaled treprostinil compared to placebo will be evaluated on the following parameters: AEs, clinical laboratory assessments, ECGs, PE findings, oxygenation, PFTs, vital sign measurements, and at-home spirometry.

All AEs as recorded by the Investigators will be assigned a Medical Dictionary for Regulatory Activities (MedDRA) Preferred Term and System Organ Class by the Sponsor for reporting purposes. The summary of AEs will include the number and percentage of subjects, as well as the number of events reported for each Preferred Term. No inferential analyses are planned for the AEs.

Data collected prior to dosing will serve as baseline values for the evaluation of data collected during the Treatment Period. Summary statistics will be calculated for measured values and changes from baseline values. Treatment-emergent changes in clinical laboratory evaluations, ECGs, oxygenation, PFTs, at-home spirometry, and vital sign measurements will be summarized by treatment group. No inferential analyses are planned on these safety endpoints.

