#### 1.2.3 Clinical Experience

A series of acute and chronic investigator-initiated clinical studies were conducted with inhaled treprostinil to optimize the formulation for inhalation; determine dose response, tolerability, and safety; and to evaluate safety and tolerability when combined with other PAH therapies (Channick 2006, Voswinckel 2006). In the acute dosing studies, administration of inhaled treprostinil resulted in pulmonary vasodilation at relatively low doses. In the chronic studies, administration of inhaled treprostinil resulted in sustained improvement of exercise capacity.

A randomized, double blind, placebo-controlled, Phase 3 study (TRIUMPH-I) was conducted to assess the safety and efficacy of inhaled treprostinil in combination with approved PAH therapies. Two hundred thirty-five subjects who were clinically stable on an approved background oral PAH therapy (bosentan or sildenafil) were randomly allocated to receive either placebo or inhaled treprostinil for 12 weeks. The primary efficacy endpoint was change in exercise capacity at Week 12 as measured by 6-Minute Walk Distance (6MWD). At Week 12, subjects receiving inhaled treprostinil had a median improvement of +21.6 meters in 6MWD and subjects in the placebo group had a median improvement of +3.0 meters. The Hodges-Lehmann placebo-corrected median change from baseline in peak 6MWD was +20.0 meters (p=0.00044). The durability of this result was supported by secondary measures related to the trough 6MWD, which was measured at least 4 hours after the last dose of inhaled treprostinil. At Week 12, trough 6MWD showed a placebo-corrected median treatment effect of 13.7 meters (p=0.0066). The most commonly reported adverse events (AEs) in the inhaled treprostinil group were cough (54%), headache (41%), and nausea (19%). There were no remarkable treatment-related changes in vital signs, physical examination (PE) findings, chest x-rays, pulmonary function tests (PFTs), or clinical laboratory parameters (McLaughlin 2010).

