#### 10 STATISTICAL CONSIDERATIONS

This section briefly describes the planned statistical analyses. A complete description of the methodology will be specified in the Statistical Analysis Plan (SAP), which will be finalized prior to database lock. Any changes in the statistical methods described in this protocol that occur prior to database lock will be documented in the SAP and will not require a protocol amendment.

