10.2 ADVERSE EVENTS

Adverse events are recorded starting from the time each subject signs the ICF until the time a screen failure is documented, study completion, or early termination. All events recorded by the Investigators will be assigned a MedDRA PT and SOC. The most recently available MedDRA version before the database lock date will be used to assign preferred terms and system organ classes. All presentations will present data by treatment received at the time of the event.

Adverse events that occur during the Washout Period following Treatment Period 1 will be presented as having occurred on the treatment taken by the subject during Treatment Period 1. Similarly, AEs that occur during post-discontinuation follow-up will be presented as having occurred on the treatment taken by the subject during Treatment Period 2. Finally, AE tabulations will allow occurrences during low dose run-in and blinded treatment to be assessed (eg, low dose treprostinil, treprostinil treated, any treprostinil, placebo treated). Non-treatment emergent AEs observed outside of any study drug exposure will not be presented.

In addition, a limited number of presentations may be tabulated for AE data by both treatments received at the time of the event and treatment sequence, including the total rates by sequence.

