10.2.5 Summary of Treatment Emergent Adverse Events

An overall summary of AEs by treatment received at the time of the event and treatment will contain the following:

- Total number of AEs, total number of subjects with at least one AE
- Total number of related AEs, total number of subjects with at least one related AE
- Total number of serious adverse events (SAEs), total number of subjects with at least one SAE
- Total number of AEs leading to study withdrawal
- Total number of AEs leading to treatment discontinuation.

Table summaries of all AEs will present numbers and percentages by SOC and PT of the following by treatment received at the time of the event:

- Subjects with at least one AE
- Subjects with at least one treatment-related AE
- Subjects with at least one SAE
- Subjects with an AE leading to treatment discontinuation.

AEs will also be summarized by treatment received at the time of the event for the following:

- AEs by severity
- AEs by relationship to treatment
- AEs by action taken with treatment, separately
- Listing of all SAEs.

Finally, a table summarizing the AEs that occurred during the pre-randomization run-in phase will be presented for all screened subjects.

Adverse events will be presented in alphabetical order of SOC and by decreasing order of incidence of the PTs.

For these summaries, a subject having the same AE multiple times will only be counted once for the corresponding PT. Similarly, a subject who experienced multiple AEs within the same SOC will be counted only once for that SOC.

A subject experiencing the same AE multiple times or at multiple severities will only be counted once under that PT at the worst severity rating. Similarly, a subject who experiences the same AE multiple times or at multiple severities across multiple PTs within the same SOC will only be counted once for the worst severity rating within the SOC.

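### The protocol promises adverse event counts for each Preferred Term, but SAP 10.2.5 as published plans only subject counts at that level and records no decision to drop the event counts

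*Protocol*

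**What the plan says.** Protocol 10.3.4 asks for two quantities at PT level: "The summary of AEs will include the number and percentage of subjects, as well as the number of events reported for each Preferred Term". The same section plans no inferential analysis of adverse events.

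SAP 10.2.5 has two layers.

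- **Overall summary.** This does count events, but across all terms together. Its first line is "Total number of AEs, total number of subjects with at least one AE". Related events and serious events get the same pair of totals. Events leading to study withdrawal and to treatment discontinuation get event totals.
- **Tables by SOC and PT.** These are introduced by "Table summaries of all AEs will present numbers and percentages by SOC and PT of the following". The four items that follow are all subjects: with any AE, with a treatment-related AE, with an SAE, and with an AE leading to discontinuation. The counting rule is "For these summaries, a subject having the same AE multiple times will only be counted once for the corresponding PT". The severity rule has the same form: "A subject experiencing the same AE multiple times or at multiple severities will only be counted once under that PT at the worst severity rating".

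SAP 10.2.5 also plans summaries by severity, relationship and action taken, and a listing of all SAEs. SAP 10.2 leaves room for optional extra tables by treatment and sequence, without mentioning events per term.

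Protocol 10 allows the SAP to depart from the protocol's methods on one condition: "Any changes in the statistical methods described in this protocol that occur prior to database lock will be documented in the SAP".

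**The concern.** A programmer who builds the PT tables from SAP 10.2.5 alone would produce subjects and percentages and stop there. The event count that the protocol promises for each term would not be delivered, and the published text does not say that this was intended.

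The omission bears on the safety comparison because no inference on adverse events is planned, so the descriptive tables are the comparison. A subject count answers how many people had the event at least once. It cannot show whether those people had it more often. Some terms that are plausible for an inhaled drug in this population, such as cough, can recur within a 12-week period. For common terms the subject percentage also compresses a difference in event rates, because anyone who has already had one event cannot be counted again.

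**Working it through.** **Setting the texts side by side.** The documents give no figure on this point, so there is nothing to reproduce. The first check is textual.

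| Quantity | Protocol 10.3.4 | SAP 10.2.5, overall summary | SAP 10.2.5, SOC/PT tables |
|---|---|---|---|
| Subjects, n and % | For each PT | Number of subjects, all terms together | Yes, once per subject per PT |
| Number of events | For each PT | All terms together | Not mentioned |

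The parallel-design appendix does not change this. SAP 12.4 says that sections it does not mention stand as written. SAP 12.4.7 replaces text for 10.1, 10.2, 10.5, 10.6 and 10.7, but not for 10.2.5. The gap is therefore the same under both designs.

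**Illustration 1: recurrence confined to the same subjects.** Inputs are 124 subjects on each treatment (the evaluable crossover number in Protocol 10.2) and 54% incidence on both (the cough rate in Protocol 1.2.3). The number of events per affected subject is assumed: 1 on placebo and 2, 3 or 5 on treprostinil.

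- Affected subjects on each treatment: 0.54 × 124 = 67 after rounding, and 67/124 = 54.0%.
- The PT row therefore reads 67 (54.0%) against 67 (54.0%) in every case.
- Placebo events: 67 × 1 = 67.
- Treprostinil events: 67 × 2 = 134, 67 × 3 = 201, 67 × 5 = 335.

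The overall total would move, but less and less as other events accumulate. With threefold recurrence of cough and 200, 400 or 800 other events on each treatment (assumed), the treprostinil/placebo ratio of all AEs is:

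- (200 + 201)/(200 + 67) = 401/267 = 1.50
- (400 + 201)/(400 + 67) = 601/467 = 1.29
- (800 + 201)/(800 + 67) = 1001/867 = 1.15

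**Illustration 2: event rate doubled, events Poisson (assumed).** The incidences in Protocol 1.2.3 come from the inhaled treprostinil arm of an earlier study in pulmonary arterial hypertension, so they are used here as active-arm values. With rate λ, the proportion with at least one event is p = 1 − exp(−λ). If placebo has half the active rate, its proportion is 1 − exp(−λ/2) = 1 − √(1 − p).

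| Term | Active p | Placebo, 1 − √(1 − p) | Subject ratio | Event ratio |
|---|---|---|---|---|
| Cough | 54% | 1 − √0.46 = 32.2% | 1.68 | 2.0 |
| Headache | 41% | 1 − √0.59 = 23.2% | 1.77 | 2.0 |
| Nausea | 19% | 1 − √0.81 = 10.0% | 1.90 | 2.0 |

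Under this assumption the attenuation is moderate for the commonest term and slight for the rarest.

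**The case against.** The strongest reply is that the SAP is silent here and does not contradict the protocol. A reader might infer that the count-once rule abolishes the event count. It does not: it says how a subject with repeats is counted, and an events column could stand beside it. The SAP presents itself as adding detail to the protocol, and no published text withdraws the commitment, so it can fairly be read as still in force. That stands. It makes this a gap to close rather than a conflict of rules. It does not supply the missing column, because the only items SAP 10.2.5 lists for these tables are subject counts.

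Second, the contents page names a list of tables (12.1) that is not in the published text, and part of the preface is redacted. A table title with event counts, or a documented change, could be there. This also stands and limits the claim to the text that can be read.

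Third, other outputs would catch part of the signal. The overall event total would rise, and repeated serious events would appear in the SAE listing. Both are true, but the total does not name the term and the listing does not cover non-serious repeats.

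Fourth, a reader might treat 54% as the comparator rate and double it, which gives 1 − 0.46² = 79% and a subject ratio of 1.46. The protocol reports 54% for the treprostinil arm, so that overstates the attenuation. A reader might also conclude that the treatment difference will be understated. That follows only if treprostinil raises event rates or recurrence, which is unknown; the documents give no recurrence rate. Subject incidence remains correct for what it measures.

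**Conclusion.** The gap holds as a minor reporting point. The protocol specifies a count of events for each Preferred Term. SAP 10.2.5, as far as it can be read, does not plan one, and the documentation that Protocol 10 requires for a changed method is not visible. Following SAP 10.2.5 as written would omit a safety output that the protocol specifies.

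The size depends on assumptions. If recurrence fell entirely in subjects already affected, the PT row would show no difference whatever the event ratio; that is the extreme case. If events were Poisson and the rate doubled, the subject ratio would be about 1.68 for cough and 1.90 for nausea, against 2.0. A reader might infer that treprostinil could look identical to placebo across the safety output. That is too strong: only the PT row can match, and only when incidence is equal.

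No hypothesis test, alpha level or sample size is touched. The individual records remain available, so the count could be produced later without new data.

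**What to change.** In SAP 10.2.5, add to the all-AE table by SOC and PT a column with the number of events, by treatment received at the time of the event, next to the subject number and percentage. State that the count-once rule applies only to the subject columns, and that this holds for both the crossover and the parallel design.

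Extending the column to the treatment-related and SAE tables is optional. A reader might take Protocol 10.3.4 to require it there too, but its sentence concerns the summary of AEs.

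If the sponsor does not want the count, the alternative is to record in the SAP that it is withdrawn, with the reason, as Protocol 10 provides.

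The cost is a short change of SAP wording and a slightly wider table. Onset and cessation of each event are already recorded (Protocol 9.2), so no new data are needed.
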